#### 8.4.1. Time Period and Frequency for Collecting AE and SAE Information

All AEs and SAEs will be collected from the signing of the informed consent form (ICF) until the follow-up visit at the time points specified in the SoA (Section 1.2).

AEs will be divided into non-treatment-emergent AEs (non-TEAEs) and treatment-emergent AEs (TEAE). Non-TEAEs are those AEs that occurred prior to the first study treatment and TEAEs are those AEs with onset date/time at or after the first study treatment.

All SAEs will be recorded and reported to the sponsor or designee immediately and under no circumstance should this exceed 24 hours, as indicated in Appendix 3. The investigator will submit any updated SAE data to the sponsor within 24 hours of it being available.

Investigators are not obligated to actively seek information on AEs or SAEs after conclusion of the study participation. However, if the investigator learns of any SAE, including a death, at any time after a participant has been discharged from the study, and he/she considers the event to be reasonably related to the study intervention or study participation, the investigator must promptly notify the sponsor.

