1. INTRODUCTION

This Statistical Analysis Plan (SAP) describes the planned analysis for Click Therapeutics study CT-132-R-001, "A Randomized Double-blind, Digital-Controlled, Parallel-Group, Virtual Study to Evaluate the Effectiveness and Safety of a Digital Therapeutic (CT-132) as Adjunctive Therapy in Late Adolescents and Adults for the Prevention of Episodic Migraine". This SAP should be read together with the protocol for full details on the study.

The SAP is intended to agree with the protocol with regard to statistical aspects that were specified in the protocol. However, the SAP may contain additional details for analyses that were defined in the protocol, and may provide details on statistical aspects that were not described in the protocol. In case of disagreement between the SAP and the protocol, the SAP prevails. Differences will be described in the statistical report and at the end of this document.

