4. STUDY DESIGN

4.1. General Design

This is a randomized, double-blind, digital-controlled, parallel-group, virtual study to assess the effectiveness and safety of CT-132 in late adolescents and adults for the prevention of migraine in comparison to a digital control. Eligible participants must report having four or more migraine days per month in the three months prior to the Screening Visit. All participants will complete an identical, pre-randomization onboarding experience, which includes verifying participant understanding of and interest in the study, and a run-in period to capture baseline MMDs within the Study App. During the run-in period and intervention period, these participants will continue to take their healthcare provider-prescribed acute and first- and second-line preventive medications for the treatment of migraine, while continuing to use the Study App to report headache and symptoms and medications. This daily reporting is referred to below as eDiary use. Upon successful completion of the onboarding experience, run-in period, and confirmation of participant interest and eligibility, the participant will be randomized at the baseline study visit. The duration of participation will be approximately 19 weeks, including an up-to-14-day screening period, a 28-day run-in period, a 12-week double-blind intervention period, and an up-to-7-day follow-up period for safety assessments.

The activities and assessments during the 2-week screening period, the 4-week run-in period, the 12-week double-blind intervention period, and the 1-week follow-up period will be completed according to the Schedule of Activities and Assessments (Protocol Section 1.2). Trial staff will implement procedures remotely. Participants will be assessed based on validated standard clinician-rated and participant-rated outcome scales for migraine at screening, the intervention period, and the follow-up period. Participants will also be evaluated for safety throughout the duration of the trial.

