7.6. Exposure

Exposure to study intervention, in days, will be calculated for each participant as number of days from first day of treatment until last day of treatment + 1. First day of treatment is defined as the first date with adherence to task and last day of treatment is defined as the last date of adherent to task.

Exposure will be summarized using descriptive statistics by treatment group.

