9. SAFETY ANALYSIS

All safety analyses will be conducted on the safety analysis set and will be descriptive.

AE will be recorded from date of signing the ICF and onwards. All AEs will be coded by system organ class (SOC) and preferred term (PT) using Medical Dictionary for Regulatory Activities (MedDRA) version 25.1.

Summaries will present non-treatment emergent AEs (AEs started before first day of treatment) and treatment-emergent AEs (TEAE; AEs started after first day of treatment) separately.

In an overview table, the number and percentage of participants who experienced a TEAE, non-TEAE, serious TEAE, treatment related TEAE, died due to an AE, or discontinued from study treatment due to a TEAE will be summarized by treatment.

The percentages of participants with TEAEs will be summarized by treatment using MedDRA preferred term nested within system organ class (SOC). Events will be ordered by decreasing frequency within SOC, and SOC with be ordered by decreasing frequency.

Similar summary will be presented for non-TEAE, serious TEAE, treatment related TEAE and TEAE related to worsening of migraine.

AEs with missing start date will be considered as a TEAE.

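### SAP 9 gives no class to an adverse event that starts on the first day of treatment, and its onset-only rule can keep a pre-treatment event that worsens out of the serious and treatment-related TEAE tables

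*SAP*

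**What the plan says.** Adverse events are collected long before the app is activated. Protocol 8.4.1 states: "All AEs and SAEs will be collected from the signing of the informed consent form (ICF) until the follow-up visit". SAP 9 then splits them into "non-treatment emergent AEs (AEs started before first day of treatment) and treatment-emergent AEs (TEAE; AEs started after first day of treatment) separately". SAP 7.6 fixes the reference point: "First day of treatment is defined as the first date with adherence to task".

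Protocol 8.4.1 draws the line differently: "TEAEs are those AEs with onset date/time at or after the first study treatment". On conflict, SAP 1 says: "In case of disagreement between the SAP and the protocol, the SAP prevails".

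The split decides what each table contains. SAP 9 provides: "Similar summary will be presented for non-TEAE, serious TEAE, treatment related TEAE and TEAE related to worsening of migraine". The seriousness, relatedness and migraine-worsening tables are therefore restricted to TEAEs. The non-TEAE summary has no stated breakdown by seriousness or relatedness. SAP 9 has one fallback: "AEs with missing start date will be considered as a TEAE".

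Neither definition mentions an event that begins before treatment and gets worse during it.

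**The concern.** The TEAE tables are where a reader looks for harm arising under the app, and the written rule leaves two holes in them.

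- **First-day onsets.** The SAP excludes the first day from both sides of the split. Taken literally, an event starting that day is in no summary that depends on the split. A programmer would probably code it as on or after, but that choice should be written down before the study is unblinded (SAP 4.4 places the final analysis after unblinding).
- **Worsening of an open event.** If an event begins in screening or run-in, is still open at first treatment, and then intensifies or becomes serious, its onset date still precedes treatment. Whether it reaches the serious or treatment-related TEAE table depends on how the site happened to record the change.

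**Working it through.** No event count can be derived from the documents. The check applies the written rules to the possible cases.

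**Step 1. Can an event be open at first treatment?** SAP 4.1 gives "an up-to-14-day screening period, a 28-day run-in period, a 12-week double-blind intervention period", followed by up to 7 days of follow-up. Time before treatment: 14 + 28 = 42 days at most. Whole collection window: 42 + 84 + 7 = 133 days = 19 weeks, which reproduces the stated duration of participation. Events are collected throughout, so some can be open at activation.

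**Step 2. Classify by onset.**

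| Onset relative to the first day of treatment | SAP 9 | Protocol 8.4.1 |
|---|---|---|
| Day before | non-TEAE | non-TEAE |
| Same day | neither | TEAE if at or after first treatment, otherwise non-TEAE |
| Day after | TEAE | TEAE |

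The middle row is the conflict. It can arise for every member of the safety set, because SAP 5.6 requires at least one completed task and each member therefore has a first task date.

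**Step 3. Does other SAP text close the gap?** The fallback in SAP 9 covers a missing start date, not a known one that falls on the first day. SAP 6.1 numbers study days from the baseline visit and says nothing about classing adverse events. SAP 7.3 includes the boundary date when it defines concomitant medication, so the SAP handles a similar boundary properly elsewhere.

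**Step 4. An event open at first treatment that then worsens or becomes serious.** There are two ways to record it.

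| How the site records it | Onset date used | Class in both documents | Where it is counted |
|---|---|---|---|
| New adverse event for the exacerbation | On treatment | TEAE | TEAE tables, including serious or related if applicable |
| Update to the original record | Before treatment | non-TEAE | Non-TEAE summary only; not in the serious or related TEAE tables |

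**Step 5. Which way does the protocol point?**

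- *Towards a new event:* the AE definitions in Protocol 10.3 and 10.7.1 include exacerbated as well as new disease. The list of qualifying events in 10.3 names exacerbation of a chronic or intermittent pre-existing condition. Protocol 8.4 makes the investigator responsible for recording whatever meets the definition.
- *Towards the original record:* the follow-up rules in Protocol 10.3.2 and 10.7.3 send new information on a reported event back to the form first submitted.
- *Not settled:* no visible sentence says which applies when the exacerbated condition is itself an adverse event already reported. Protocol 10.3.2 asks for an intensity category for each event, but does not ask for dated changes of intensity.

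**The case against.** The strongest reply has four parts.

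1. **Exacerbations are already adverse events.** Taken together, Protocol 8.4, 10.3 and 10.7.1 tell the investigator to record an on-treatment exacerbation, and it would then carry an on-treatment onset. The follow-up rules concern further information on an existing report and do not say that a worsening keeps the old date. This largely stands. A reader might infer that every pre-treatment event that worsens is lost from the TEAE tables; the documents do not support that. What remains is the event updated on its original record.
2. **The protocol fills the first-day gap.** SAP 1 says the SAP is meant to agree with the protocol and be read with it, so the protocol's inclusive wording could apply. This is a fair reading, but the SAP's wording is a stated rule rather than silence, and its precedence clause points the other way. Two programmers could reasonably code it differently.
3. **The migraine-worsening table is hardly affected.** A reader might infer that this table is the main casualty, because Protocol 2.3.1 names worsening migraine as the principal risk. That does not follow. Protocol 10.3 excludes expected symptoms of the studied disease from adverse events, so ordinary run-in migraine rarely opens a record with a pre-treatment onset. Worsening beyond expectation would usually become an adverse event for the first time on treatment. This stands.
4. **Little disappears altogether.** Protocol 9.4.8 counts all AEs, SAEs, related events and AE-related discontinuations through the study. SAP 9 counts deaths due to any AE, and SAP 7.1 gives discontinuations by reason. An affected pre-treatment event also appears in the non-TEAE summary. This stands, although none of these displays isolates worsening on treatment.

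**Conclusion.** The point holds in limited form. The first-day gap is a plain drafting error in SAP 9 that conflicts with Protocol 8.4.1. The onset-only rule is a real but narrower weakness, confined to events that open before treatment, are still open at first treatment, worsen or become serious afterwards, and are not entered as new.

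The number of such events is probably small and cannot be computed. A reader might take the 42 pre-treatment days out of 133 (31.6%), or the one first day out of 84 intervention days (1.2%), as the share of events affected. These are shares of calendar time. They show that opportunity exists and do not measure lost events. Safety analyses are descriptive, the primary analysis is untouched, and events open at activation should be balanced between arms in expectation.

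The conclusion assumes that some sites would update an original record, and that the CRF guidance mentioned in Protocol 10.1.7, the SAP table and listing sections and SAP Appendix A do not already settle the matter; none of these is visible. This is a low-priority, inexpensive improvement.

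**What to change.** Change SAP 9 only. Define a TEAE as an adverse event that either:

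- has its onset on or after the first study treatment, where a first-day onset with no recorded time counts as a TEAE; or
- has an earlier onset and increases in intensity or becomes serious on or after the first study treatment.

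Everything else is a non-TEAE. Use the definition in every TEAE table. Treating a first-day onset of unknown time as a TEAE follows the direction SAP 9 already takes for missing start dates.

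Through CRF guidance, tell sites to record such a worsening as a new adverse event row with its own onset date. This makes the second limb workable, because an undated change on an old record could not be classified.

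The cost is one definition in the SAP and one line of site instruction. A reader might infer that Protocol 8.4.1 must be amended too; it need not be, since the SAP prevails and its text can carry the whole definition. The downside is that TEAE counts may rise slightly in both arms.

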5.6. Safety Analysis set

The safety analysis set includes all randomized participants who are exposed to the study intervention (completed at least one task). Participants will be analyzed according to the intervention they received. This analysis set will be used for all safety analyses.

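### SAP 9 counts every AE with a missing start date as treatment-emergent, even where its end date or first report shows that it preceded treatment (minor)

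*SAP*

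**What the plan says.** SAP 9 reports non-treatment-emergent and treatment-emergent AEs in separate summaries. It closes with a rule for undated events: "AEs with missing start date will be considered as a TEAE". In the text available, the rule does not mention the end date of the event or the visit at which it was first reported.

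AE collection starts well before treatment. SAP 9 says "AE will be recorded from date of signing the ICF and onwards", and Protocol 8.4.1 says "All AEs and SAEs will be collected from the signing of the informed consent form (ICF) until the follow-up visit". The Schedule of Activities (Protocol 1.2) marks AE collection at screening, run-in and baseline as well as at every later visit.

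The protocol classifies AEs by when they occurred. Protocol 8.4.1 says "Non-TEAEs are those AEs that occurred prior to the first study treatment", and that "TEAEs are those AEs with onset date/time at or after the first study treatment".

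SAP 1 settles any conflict: "In case of disagreement between the SAP and the protocol, the SAP prevails".

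**The concern.** A blank start date does not always mean that timing is unknown. If the AE has an end date in the run-in period, or was first reported at a run-in contact, the record itself shows that it began before the assigned app could have been used. The SAP sentence ignores that evidence and tells the programmer to file the event as treatment-emergent.

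What is at stake is the correct classification of individual events. An event from before randomisation would be shown under an arm whose app was not yet active. The overall TEAE table and the table of TEAEs related to migraine worsening are the most plausible places for this. Migraine worsening is a named safety endpoint (Protocol 3, SAP 3.4). Participants must have 4 to 14 migraine days in the run-in, and the protocol's AE definition in Appendix 3 includes an increase in the frequency of an intermittent pre-existing condition. Reports of worsening during run-in are therefore possible, and the onset of a gradual worsening can be hard to date.

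**Working it through.** The plan gives no figure on this point, so the check is mainly a comparison of the two rules.

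**Who is affected.** The TEAE tables use the safety set: "The safety analysis set includes all randomized participants who are exposed to the study intervention (completed at least one task"). Undated AEs in screen failures never reach these tables. Only pre-treatment AEs of people who were later randomised and treated matter here.

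**Three kinds of AE with a missing start date in that set:**

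1. *The end date is before the first day of treatment.* Onset cannot be later than the end, so the AE came before treatment. Protocol 8.4.1: non-TEAE. SAP 9: TEAE. The documents conflict.
2. *The AE was first reported at screening, in run-in, or at the baseline visit before activation.* An event cannot be reported before it starts, so it came before treatment. Protocol 8.4.1: non-TEAE. SAP 9: TEAE. The documents conflict.
3. *The AE was first reported after activation, and its end date is missing or falls on or after the first day of treatment.* Onset is truly unknown. SAP 9: TEAE. This is a cautious default and does not contradict the protocol.

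In cases 1 and 2 the precedence clause in SAP 1 makes the SAP result the one that is programmed.

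**Comparison within the SAP.** SAP 7.3 already uses end dates for medications. One that ended before baseline is previous therapy; one that ended on or after baseline, or has no end date, is concomitant. Applying the same test to AEs would bring in no new convention.

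**Possible size (illustration on assumed values).** The documents give neither AE rates nor rates of missing dates. Take 558/2 = 279 participants per arm, true TEAE risks of 20% and 30%, and a share m of participants in each arm who have a case 1 or case 2 record. The reported risk in an arm becomes p + (1 − p)m, so the risk difference becomes (0.30 − 0.20)(1 − m).

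- m = 0.5%: 0.204 and 0.3035; difference 9.95 points; extra participants 279 × 0.80 × 0.005 = 1.1 and 279 × 0.70 × 0.005 = 1.0.
- m = 2%: 0.216 and 0.314; difference 9.8 points; extra participants 279 × 0.80 × 0.02 = 4.5 and 279 × 0.70 × 0.02 = 3.9.

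Against a true difference of 10.0 points, the contrast hardly moves.

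**The case against.** The strongest reply is that counting undated AEs as treatment-emergent is a normal cautious convention, and that the problem needs a record nobody has shown to exist: no start date, but an end or report date before treatment. Investigators must record all relevant AE information (Protocol 10.3.2), and the sponsor checks data quality (Protocol 10.1.7). This stands as a limit on size. It does not repair the rule, because the convention is justified by unknown onset, and in cases 1 and 2 the onset is known to precede treatment.

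A second reply is that the public text is incomplete. The content of SAP Appendix A (Data Specifications) is not shown, and a date rule there cannot be excluded. However, SAP 9 does not point to it, and SAP 8 cites it only for headache qualification and for deriving MMDs and MHDs. For the same reason nothing is claimed here about partial dates.

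Three stronger readings are tempting, and the documents support none of them:

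- *That about a third of undated AEs would be misfiled.* On Schedule of Activities days, 42 of 42 + 92 = 134 collection days (31%) precede treatment. To turn that into a misfiling rate, one must assume that undated AEs are spread evenly over periods of maximum length. It also counts every undated pre-treatment AE, not only those that the record shows to be pre-treatment.
- *That the rule meaningfully dilutes the comparison between arms.* Events before randomisation are balanced in expectation, and the illustration shows a shift of at most 0.2 points.
- *That such events would fill the treatment-related table.* The investigator assesses causality for each AE and considers its timing relative to the intervention (Protocol 10.3.2), so an event that ended before activation would rarely be judged related.

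**Conclusion.** Wrong as written, and minor. The unconditional sentence in SAP 9 gives a classification that contradicts Protocol 8.4.1 for any undated AE whose end date or first report precedes treatment, and SAP 1 makes that classification binding. The number of such records is not given and is probably very small. The safety analyses are descriptive, so no test, error rate or success criterion depends on this, and the primary conclusion is unaffected. The finding rests on the SAP text as published, and its practical effect depends on at least one such record occurring in the safety set.

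**What to change.** Replace the last sentence of SAP 9 with:

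*An AE with a missing start date is considered a TEAE unless its end date is before the first day of treatment, or it was first reported at or before the baseline visit, prior to activation of the assigned Study App; it is then a non-TEAE.*

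The second condition refers to activation because a date comparison alone would fail at the baseline visit. Randomisation and activation take place there, and the first task may be done on the same day. A run-in AE first mentioned at that visit would then not have a report date earlier than the first day of treatment.

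AEs with no usable date remain TEAEs, so the cautious default is kept. The cost is one SAP sentence and one programming condition, best settled before unblinding. The end-date test uses the same logic as SAP 7.3. The second test assumes that the visit of first report, and whether it came before activation, can be read from the AE record; the documents do not say, so data management should confirm it.

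While the section is open, the boundary wording should also be aligned. SAP 9 defines "treatment-emergent AEs (TEAE; AEs started after first day of treatment) separately" and non-TEAEs as starting before that day, so an AE that starts on the first day falls in neither group, whereas the protocol counts onset at or after first treatment.

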10.2. Figures

Figures will be numbered in a similar manner to the tables.

10.3. Listings

0	

CT-132-R-001, Statistical Analysis Plan

- 11. APPENDIX
- 11.1. Appendix A -
